### 13.6 Methodology to Identify IFI and IA

The EORTC/MSG guidelines incorporate clinical, microbiologic, histopathologic, and radiographic data for classification of proven or probable IFI or IA. Therefore, in order to establish these diagnoses, the following data will be obtained (according to the IFI checklist (Section 10.2): pathology reports (including autopsy reports), CT scan and MRI reports, fungal gram stain and microbiology culture results, non-culture mycology testing results (i.e. histoplasma urine antigens, cryptococcal CSF and serum antigens), ophthalmology exams, and bronchoscopy reports. An independent data review committee including infectious disease and oncology experts who are unaware of treatment assignments will review and classify all cases of fungal infection according to the consensus criteria of the EORTC/MSG.

#### 13.6.1 Justification of Methodologic Choices

##### 13.6.1.1 Justification for Chosen Thresholds for Platelia *Aspergillus* EIA and Fungitell Assay

IFI outcomes are often devastating, thus it would be desirable to optimize sensitivity at the potential expense of specificity. Furthermore, a highly sensitive test will likely result in a high negative predictive value. Clinicians caring for patients with positive tests would then have a heightened concern for IFI while a negative test result would reassure them that no further modifications to antifungal therapy are necessary at that time. It was with these intentions that the following threshold values were chosen to conclude negative and positive results for each biomarker.

The level of  $\geq 0.5$  GM index for Platelia *Aspergillus* EIA will be the established threshold to determine a positive result. This is the level that was established for FDA approval during testing in adults. The operating characteristics of this test have been evaluated in pediatric and adult patients using various cutoffs ranging from 0.5 to 1.5 as well as using single and consecutive positive results. Increasing the threshold level and requiring multiple consecutive positive results often reduced the sensitivity while optimizing specificity. As noted above, our goal is to optimize sensitivity and negative predictive value, at the risk of lower specificity and positive predictive value. Therefore, the lower threshold of  $\geq 0.5$  on a single test was chosen.

The Fungitell Assay threshold result of  $\geq 80$  pg/mL was chosen based on manufacturer recommendations and available data. For two adult studies that evaluated this test, the cut-off for a positive test was lowered to  $> 60$  pg/mL. Lowering of the manufacturer threshold in these two studies resulted in high sensitivity which would be consistent with the goals of our study. However, analysis of BG levels in 120 healthy children revealed that 22% of them had BG levels greater than 60 pg/mL. Although this level would optimize sensitivity, the likelihood for false positivity is too high. There were still 15% of healthy children in this study that had a level of  $\geq 80$  pg/mL. This suggests that even at a level of  $\geq 80$  pg/mL, sensitivity of this assay in children would be preserved. Therefore, the manufacturer threshold of  $\geq 80$  pg/mL was chosen. For both biomarker assays, a post hoc analysis of various cutoffs as well as assessment of sequential positive testing will be performed in an attempt to identify the most ideal cut-off for future use of this assay as an integral biomarker (please see statistical analysis below).

##### 13.6.1.2 Justification for IFI Gold Standard

We have chosen to use EORTC/MSG defined proven or probable IA or IFI (Appendix II) as the gold standard. The ideal gold standard to compare to each biomarker would be a positive culture of a fungal organism from blood or infected tissue. However, there are significant challenges to establish the presence of fungal infection with isolation of the etiologic organism. Certain molds such as *Aspergillus*

do not grow routinely in blood cultures, the ability to obtain tissue for culture can be impacted by the size and location of a visceral lesion, and the clinical status of a patient may preclude invasive procedures to obtain cultures. Therefore, an alternate endpoint to identify all patients who truly have IFI is necessary. This issue has been addressed by the EORTC/MSG. This group of experts initially created criteria based on clinical, radiographic and culture data to define possible, probable and proven IFI in 2002 and revised these criteria in 2009. These criteria have served as the primary endpoint for major trials of antifungal drug efficacy, in strategy trials, for formulating clinical practice guidelines, as well as for undertaking epidemiologic studies. Consistent use of these criteria as the primary endpoint will allow for comparison of the resultant data to prior and future studies.

### 13.7 Factors resulting in False Positive Results

A number of medications, medical interventions, and infections have been suggested as possible causes of false positive results for BG and GM testing. Table 3 lists the potential causes of false positive results reported in the literature. It is anticipated that patients being treated for AML will have reason to be exposed to a number of these medications, infusions and/or medical interventions. Additionally, *Pneumocystis jiroveci* infection is also considered a cause of a “false positive” BG test. Technically this is not a true false positive as the Fungitell Assay is detecting BG from the cell wall of *Pneumocystis jiroveci* as it would for other fungal infections. However, in this instance it is considered a false positive as the treatment of choice for this infection is trimethoprim-sulfamethoxazole as opposed to a typical anti-fungal agent. A sensitivity analysis (as described in Section 13.8.4 below) will be performed to investigate the impact of these false positive rates on the operating characteristics of the 2 biomarkers.

**Table 3.** Potential factors resulting in false positive testing for (1→3) beta-D glucan and GM assays

Factor	(1→3) Beta-D Glucan Assay	Galactomannan EIA Assays
Medications	Amoxicillin-clavulanate	*Piperacillin-Tazobactam *Amoxicillin-clavulanate
Infusions	*Intravenous immune globulin *Cellulose filters for IV infusion *Albumin	*Plasmalyte (electrolyte infusion) *Intravenous solution with sodium gluconate
Medical interventions	*Hemodialysis with cellulose filter *Gauze packing on serosal surfaces	*Enteral feeding with soybean proteins
Other infections	* Pneumocystis jiroveci	* Penicillium spp. * Histoplasma capsulatum * Geotrichum * Neosartoria

### 13.8 Statistical Design

#### 13.8.1 Sample Size and Estimated Event Rates

The parent trial comparing prophylaxis with caspofungin to fluconazole in newly diagnosed AML patients anticipates enrollment of at least 275 patients for each arm with a total cohort of approximately 550 patients. As noted above we anticipate that at least 80% of the patients enrolled in the parent trial will also be enrolled in this ancillary study. This will result in 220 patients from each study arm. Consent for testing will be included as a part of the parent trial enrollment, thus significantly limiting the need for additional resources to complete this biomarker study.

The estimated number of probable or proven IFI events for final analyses will be different for both proposed biomarkers as they account for different types of fungal infections and the incidence for each will vary by study arm. The Fungitell Assay has the potential to identify most pathogenic fungi and thus a majority of the probable or proven IFIs will be considered as true events (excluding IFIs from *Zygomycetes* and *Cryptococci*). The Platelia *Aspergillus* EIA is specific for *Aspergillus* and thus only probable or proven IA will be considered as true events for that analysis.

Based on Section 9.3.3 of the parent trial the estimated incidence of IFI for patients in the fluconazole group is 8% and 2% in the caspofungin arm. Assuming the enrollment of 220 patients in each study arm, there would 18 IFI events in the fluconazole group and 4 IFI events in the caspofungin group. Based on data from the CCG 2961 AML trial, one-third of microbiologically proven fungal infection were the result of *Aspergillus*. Therefore, it is estimated that 6 of the 18 IFI events in the fluconazole group will be IA and between 1 and 2 of the IFI events in the caspofungin group will be IA.

#### 13.8.2 Sensitivity, Specificity, PPV, and NPV

The validity of a biomarker is based on whether the study appropriately categorizes patients with and without the illness in question (sensitivity and specificity). Alternatively the validity of a test can be measured by how well the test results predict the presence or absence of the disease (PPV and NPV). Collectively, sensitivity, specificity, PPV, and NPV are often referred to as the test's operating characteristics with the sensitivity and NPV being the most clinically relevant parameters for this study. Each component of the operating characteristics will be calculated based first on the entire cohort. As indicated in the sample size estimates above the incidence of IFI will vary between the two study arms. It is well documented that variations in the incidence/prevalence of a disease will impact the operating characteristics of a diagnostic test specifically for the PPV and NPV. Therefore, each assay's sensitivity, specificity, PPV and NPV will also be calculated separately for each study arm.

The operating characteristics for both the Platelia *Aspergillus* EIA and the Fungitell Assay will be computed at the patient level for each of the sub-aims as follows:

- a) Outcome of IA only **or** all IFI defined as a single positive test for either the Platelia *Aspergillus* EIA **or** the Fungitell Assay as compared to the EORTC/MSG criteria for proven or probable IA only **or** all IFI.
- b) Outcome of IA only defined as a single positive test for Platelia *Aspergillus* EIA only as compared to the EORTC/MSG criteria for proven or probable IA only.
- c) Outcome of all IFI defined as a single positive test for the Fungitell Assay as compared to the EORTC/MSG criteria for all proven or probable IFI.

Sensitivity, specificity, PPV and NPV and their accompanying 95% confidence intervals will be calculated using STATA statistical software version 11.0 (College Station, TX). As noted above, these parameters will first be calculated for the entire cohort and then for each study arm separately. The latter analyses are important as the incidence of IFI may vary by study arm thus impacting the interpretation of the assay results. A patient with multiple episodes of IFI will only be included in the analyses as a single IFI.

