**7.0 EVALUATIONS/MATERIAL AND DATA TO BE ACCESSIONED**

Timing of protocol therapy administration, response assessment studies, and surgical interventions are based on schedules derived from the experimental design or on established standards of care. Minor unavoidable departures (up to 72 hours) from protocol directed therapy and/or disease evaluations (and up to 1 week for surgery) for valid clinical, patient and family logistical, or facility, procedure and/or anesthesia scheduling issues are acceptable per COG administrative Policy 5.14 (except where explicitly prohibited within the protocol).

All baseline studies must be performed prior to starting protocol therapy unless otherwise indicated below.

**7.1 Required and Optional Clinical, Laboratory and Disease Evaluations  
Obtain prior to start of phase unless otherwise indicated.**

STUDIES TO BE OBTAINED	Baseline	Course 1 #	Subsequent Courses #	End of ACCL0933 Therapy
REQUIRED				
History	X			
Physical Exam (Ht, Wt, BSA)	X			
CBC, differential, platelets	X	X	X	X
Creatinine, SGPT, SGOT, bilirubin	X	X	X	X
IFI checklist		X*	X*	X*
OPTIONAL				
Sample for SNP Genotyping		X %		
GM, BG Assays		2x weekly @	2x weekly @	

# Course 1 of fluconazole or caspofungin follows Course 1 of AML therapy. *Subsequent Courses* refers to protocol-directed antifungal prophylaxis, not AML therapy.

\* Submit relevant IFI checklist documents via the Document Imaging System: [contact] at the end of each course of protocol therapy. See Section 10.2 for further details.

% Obtain at end of Course 1, optimally when the patient has ANC > 1000/ $\mu$ L and no circulating blasts.

@ Collect specimens twice weekly during the period of neutropenia (until ANC > 100-500/ $\mu$ L). See Section 13.1 for specimen collection details. It is suggested that specimens be obtained on Mondays and Thursdays but other days are acceptable if more convenient. A minimum of 2 days should separate each specimen collection. All specimens must be collected in the specimen vials provided by MiraVista Laboratories in the shipped lab collection kits. Alternative specimen vials should never be used as they may contribute to false results.

**This table only includes evaluations necessary to answer the primary and secondary aims. Obtain other studies as indicated for good clinical care.**

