## 8.0 CRITERIA FOR REMOVAL FROM PROTOCOL THERAPY AND OFF STUDY CRITERIA

### 8.1 Criteria for Removal from Protocol Therapy

- a) Development of proven or probable IFI including IA according to institutional diagnosis.
- b) Patients who begin conditioning for HSCT.
- c) Begin a new chemotherapy regimen for AML that is refractory to, or relapsed with current AML chemotherapy.
- d) Refusal of further protocol therapy by patient/parent/guardian.
- e) Recovery from neutropenia following completion of the final planned AML chemotherapy course .
- f) Physician determines it is in patient's best interest.

Patients who are off protocol therapy are to be followed until they meet the criteria for Off Study below. Follow-up data will be required unless consent was withdrawn. A patient that is placed on empiric fungal therapy for prolonged fever and neutropenia should NOT be removed from protocol therapy for subsequent AML chemotherapy courses unless one of the off protocol therapy criteria is met.

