##### 13.1.2 Sample Collection

Whole blood samples will be collected twice weekly during the period of neutropenia (until ANC > 100-500/ $\mu$ L). It is suggested that specimens be obtained on Mondays and Thursdays but other days are acceptable if more convenient. A minimum of 2 days should separate each specimen collection.

In order to perform both assays on a single specimen (Platelia™ Aspergillus EIA and Fungitell® beta-D glucan assay), collect 5 mL of whole blood in a gold top serum-separator tube (provided by MiraVista) and label with the site number, COG ID number, and date (labels will be provided with the sample shipping kit). Although the above volume of blood testing will likely represent a small fraction of the blood testing performed during the period of 1 week, it may result in an important increase in certain patients (i.e., smaller children or anemic children). Therefore, we have set the following maximum limits per kilogram for blood draws related to this ancillary study: 3 mL of blood/kg body weight in an 8 week period.

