### 13.4 Patient Accrual

All patients enrolled on ACCL0933 will be offered the chance to participate in the anti-fungal screening study. We anticipate that at least 80% of the patients in the parent trial will enroll in this ancillary study resulting in an estimated 440 patients at baseline. Those who consent will undergo Platelia *Aspergillus* EIA and Fungitell Assay testing. Blood sampling will be conducted twice weekly during anti-fungal prophylaxis treatment after each course of chemotherapy.

Each patient will have the potential for multiple courses of chemotherapy with each course having variable durations of neutropenia. Based on data from the AAML0531 trial, we have estimated the number of patients progressing from the first course of chemotherapy through the fourth course of therapy as well as duration of neutropenia for each course (see Table 2). Given a planned frequency of biomarker testing of twice per week, estimates of the number of Platelia *Aspergillus* EIA and Fungitell Assays performed during each chemotherapy course are provided (see Table 2).

**Table 2.** Estimated number of Platelia *Aspergillus* EIA and Fungitell Assay performed per course.

Chemotherapy course	Estimated Duration of neutropenia* (days)	# of testing time points for 1 patient during neutropenia †	Platelia EIA	Fungitell Assay
I (n=440)	20	6	2640	2640
II (n=380)	18	5	1900	1900
III (n=337)	17	5	1685	1685
IV (n=216)	28	8	1728	1728
Total	-	-	7953	7953

\*Based on median duration of neutropenia for each course from AAML0531 trial

†Based on a plan for 2 tests per week during neutropenic period

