#### 13.8.3 Receiver Operator Characteristics Curve

In addition to understanding the operating characteristics of a diagnostic test at a single defined threshold, it is also important to understand how variations in the test's threshold can alter the test's operating characteristics. The receiver operating characteristics (ROC) curve is a useful approach to illustrate how these operating characteristics will change as the threshold changes. Therefore, a receiver-operating-

characteristics (ROC) curve will be generated with a series of sensitivities and specificities derived from various cutoff values. For the Platelia *Aspergillus* EIA cutoffs of > 0.5, 1.0, 1.5 and 2.0 will be used. For the Fungitell Assay cutoffs of  $\geq 40$ ,  $\geq 60$ ,  $\geq 80$ , and  $\geq 100$  pg/mL will be used to create the ROC. The ROC curve will be displayed graphically (sensitivity vs. 1-specificity) and evaluated numerically (c-statistic). The c-statistic (also referred to as the area under the curve (AUC)) varies from 0.5 to 1.0 and is a measure of the test's ability to discriminate between patients with and without the gold standard diagnosis. A c-statistic of 0.5 is possible by chance alone while a perfectly discriminating test will result in a c-statistic of 1.0.

Additionally, the ROC curves will be used in an exploratory analysis to identify the threshold for each biomarker assay that optimizes the diagnostic test's sensitivity while maintaining a reasonable specificity. The identified thresholds will be used to categorize each patient as "likely to have IFI or IA" and "not likely to have IFI or IA". Once these 2 sub-groups are defined we will calculate the incidence rates of IFI or IA for each sub-group and compare them. Because the anticipated incidence for IFI and IA may be variable between the two study arms (those receiving fluconazole and those receiving caspofungin) this approach will have to be done at the level of each study arm. The incidence rates will be compared statistically using Pearson's Chi-square analysis.

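### Patients with IFI probably contribute fewer assay samples than patients without it, so any-positive scoring biases the case/non-case comparison downward and 0.5 is not the chance c-statistic

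*Combined protocol and SAP*

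**What the plan says.** Section 13.8.2 sets the unit of analysis: operating characteristics "will be computed at the patient level for each of the sub-aims". The positivity rule for beta-D glucan is "defined as a single positive test for the Fungitell Assay", and galactomannan and the combined rule follow the same pattern. Repeat infections are collapsed: "A patient with multiple episodes of IFI will only be included in the analyses as a single IFI". No look-back window, index date or adjustment for number of tests is given.

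Section 13.8.3 builds the ROC curve from sensitivities and specificities at several cutoffs and gives the benchmark: "A c-statistic of 0.5 is possible by chance alone while a perfectly discriminating test will result in a c-statistic of 1.0".

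Four places bear on how long a patient is sampled:

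- Section 13.4: "Blood sampling will be conducted twice weekly during anti-fungal prophylaxis treatment after each course of chemotherapy".
- Section 7.1, footnote to the schedule: a subsequent course "refers to protocol-directed antifungal prophylaxis, not AML therapy".
- Section 8.1(a), among the reasons for ending protocol therapy: "Development of proven or probable IFI including IA according to institutional diagnosis".
- Section 13.1.2: "Whole blood samples will be collected twice weekly during the period of neutropenia". Section 7.2.1 and another footnote in Section 7.1 also define sampling by neutropenia.

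No section says what happens to sampling after an IFI diagnosis.

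**The concern.** The chance that at least one test is positive rises with the number of tests. Taken together, Sections 13.4, 7.1 and 8.1 imply that a patient diagnosed with IFI leaves the sampling schedule, while a patient without IFI continues through as many as four courses. Cases would then have fewer chances to test positive because they are cases.

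What is affected is the comparison of cases with non-cases: sensitivity set against the false-positive rate, the c-statistic, and the predictive values and exploratory cutoff search that depend on them. The ancillary study is meant to show whether these assays can guide antifungal decisions in later trials (Sections 13.2.5 and 13.9). Part of what it measures would be how many courses a patient received. A marker with modest real signal could be judged against a chance line that is too high.

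**Working it through.** **Inputs (Section 13.4, Table 2).** Patients reaching courses I–IV: 440, 380, 337, 216. Tests per course: 6, 5, 5, 8.

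**Reproducing the plan's figure.** 440×6 + 380×5 + 337×5 + 216×8 = 2640 + 1900 + 1685 + 1728 = 7953, as Table 2 states. A patient who completes all four courses has 6+5+5+8 = 24 tests.

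**Tests per patient overall.** 7953/440 = 18.1. By last course reached, 60, 43, 121 and 216 patients have 6, 11, 16 and 24 tests. With only about 22 expected IFI in 440 (18 + 4, Section 13.8.1), this distribution is used for non-cases.

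**Tests per case.** Assume IFI is equally likely at each at-risk sampling point, in line with the roughly even incidence assumed in Section 9.3.3.

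- Sampling stops at diagnosis. The position numbers within courses I–IV sum to 21, 45, 70 and 164. Mean = (440×21 + 380×45 + 337×70 + 216×164)/7953 = 85354/7953 = 10.7.
- Sampling runs to the end of that course. Mean = (2640×6 + 1900×11 + 1685×16 + 1728×24)/7953 = 105172/7953 = 13.2.

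**Chance c-statistic, continuous marker.** For an uninformative marker with independent results, a case with m tests has a higher maximum than a non-case with n tests with probability m/(m+n). Averaging over the distributions above:

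| Sampling of cases | Mean tests per case | Chance c-statistic |
|---|---|---|
| Stops at diagnosis | 10.7 | 0.36 |
| Stops at end of that course | 13.2 | 0.42 |
| Continues through all later courses | 20.5 | 0.54 |

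**Any-positive rates, uninformative assay.** P(at least one positive) = 1 − (1 − p)^tests. The per-test rate p in this cohort is not given, so a range is shown, with sampling stopping at diagnosis:

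| p | Cases positive | Non-cases positive | Difference (points) |
|---|---|---|---|
| 1% | 10.0% | 16.4% | −6 |
| 2% | 18.8% | 30.0% | −11 |
| 5% | 39.1% | 58.0% | −19 |
| 15% | 71.7% | 90.2% | −18 |

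If sampling runs to the end of the course, the differences are −4, −7, −12 and −9 points.

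**Few cutoffs.** With one cutoff the trapezoid c-statistic is 0.5 + (sensitivity − false-positive rate)/2. With sampling stopping at diagnosis, p = 1% gives 0.5 + (0.100 − 0.164)/2 = 0.47, and p = 2% gives 0.5 + (0.188 − 0.300)/2 = 0.44.

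**Within-patient correlation (beta-binomial, p = 15%, sampling stops at diagnosis).** Intraclass correlations of 0.1, 0.3, 0.5 and 0.8 give differences of −16, −10, −6 and −2 points. The sign holds, and the effect vanishes only when all of a patient's tests agree.

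**Would scoring by course solve it?** Not if sampling stops at diagnosis, because the case's course is cut short as well. The same Table 2 weights give about 3.5 tests in a case-course against 5.8 in a non-case course (7953/1373), and a chance c-statistic of 0.36.

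**The case against.** **The stop in sampling is an inference.** A reader might take it as settled that infected patients are no longer sampled from the day of diagnosis. The documents do not say so. Sections 7.1, 7.2.1 and 13.1.2 also define sampling by neutropenia. If sampling runs to neutrophil recovery in that course, the effect is smaller (0.42). If cases are sampled through all later neutropenic courses, it does not arise (0.54), although Section 13.4 and the Section 7.1 footnote point against that. The trigger is also institutional diagnosis, whereas case status comes from central review, so an IFI recognised only centrally would not end sampling. This objection stands, and it is a reason to state the rule.

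**Specificity is not biased.** A reader might infer that it is pulled downward. It is calculated from non-cases alone, so cases stopping early cannot change it. The share of IFI-free patients never flagged over the whole schedule is a legitimate description of a screening strategy. This stands too.

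**The larger sizes are upper-end.** The 15% in Section 13.6.1.1 is the share of healthy children with a high beta-D glucan level, not a per-test rate here. If high levels are a trait of the child, within-patient correlation would be strong. The planned curve uses four cutoffs, not a full continuous ROC. The limit of 3 mL/kg per 8 weeks (Section 13.1.2) restricts counts in small children: 30 mL for a 10 kg child, or six 5 mL draws. Only 216 of 440 patients reach 24 tests. All of this reduces the size and none of it reverses the direction.

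**Existing analyses do not cover it.** The sensitivity analyses in Section 13.8.4 concern local testing and causes of false positives. Requiring two consecutive positives (Section 13.8.3) still gives longer-sampled patients more opportunities. Results by arm address prevalence.

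**Conclusion.** The point holds as a problem of comparability. If sampling follows protocol prophylaxis, as Sections 13.4 and 7.1 indicate, cases contribute about 11 to 13 tests against a cohort average of 18, and 0.5 is not the value an uninformative assay would return under the planned scoring. For a continuous marker with independent tests the chance value is about 0.36 (stop at diagnosis) or 0.42 (end of course). With stopping at diagnosis and one cutoff at 1–2% positives per test it is about 0.47–0.44, and correlation within patients moves it closer to 0.5.

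These sizes rest on Table 2, on IFI spread evenly over sampling points, and on assumed per-test rates and correlations that the documents do not give for this cohort. A reader might go further and conclude that a useful assay will be reported as worse than chance. The documents do not support that: the mechanism lowers the c-statistic, but by how much for a real marker cannot be determined from them. This is an optional ancillary study with about 22 events, so the matter is worth correcting but does not bear on the trial's primary comparison.

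**What to change.** 1. In Sections 13.1.2 and 13.4, state whether assay sampling continues after an IFI diagnosis and, if so, until when. Align the neutropenia-based and prophylaxis-based wording.
2. In Sections 13.8.2 and 13.8.3, add an equal-opportunity analysis. Take each case's results up to diagnosis, for example the highest value in a fixed look-back. Compare them with those of patients still IFI-free and being sampled at the same course and sample number, truncated at the same point. Cluster the intervals by patient.
3. Take the c-statistic, and any judgement against 0.5, from that analysis.
4. Keep the patient-level figures, labelled as the performance of the whole screening schedule.
5. Do not make untruncated course-level scoring the main analysis, since it keeps the imbalance if sampling stops at diagnosis.

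No new samples are needed: collection dates are on the specimen labels (Section 13.1.2) and course numbers on the therapy delivery maps (Sections 4.2.1 and 4.3.1). The cost is protocol and SAP wording, some programming and one more table. With about 22 events the intervals will be wide.
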